## **Sample size calculation and estimated duration of the study**

Sample size calculation is based on the incidence of NEC, as the rarest of the events that will be studied, which is currently about 15% among extremely preterm infants at our unit, as mentioned above. For study power of at least 70%, confidence level of 5%, and an expected decrease of NEC incidence from 15% to 8%, each study arm should include about 100 participants (29). Each year, our unit treats about 70 infants born in GA 22+0 – 26+6. Supposing a participation rate of 70%, it is estimated that the recruitment period should last between 3 and 4 years, preliminarily starting during 2018. However, a recruitment period of maximum 5 years will be allowed.

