### Primary outcomes

- TFF, defined as the period between birth and achievement of enteral nutrition of 170ml/kg/d.
- NEC, Bell stage II or more

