### **Completion of the study**

The study will be completed when the number of 100 subjects per study arm is reached (a maximum of 130 subjects per study arm will be allowed), estimated to be achieved by the year 2022 (and not later than year 2023).

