### **Statistical analysis**

Numerical data with a gaussian distribution will be expressed as means (standard deviation), otherwise as medians (ranges). We will use the Anderson-Darling test to assess the normality of the data. Numerical values will be compared between intervention and control groups using t-tests or the Mann-Whitney U test. Categorical variables will be compared using  $\chi^2$  or Fisher's exact tests. Times to achieve full enteral feeding will be compared by the log rank test. Multiple Cox regression analysis will be used to adjust for covariates, such as gestational age and birth weight. IBM SPSS software (current version at the time of publication) will be used for all calculations and a p-value of <0,05 will be considered significant.

Interim analysis will be conducted when 35 infants have been recruited in each study arm (estimated about 1,5 years from study start). Another interim analysis will be conducted when 65 infants have been recruited in each study arm (estimated about 3 years from study start). Unplanned interim analysis will also be conducted in case of subjectively estimated too obvious difference between the groups regarding the primary outcomes, at any time during the study. The study will be discontinued as soon as an interim analysis shows statistically significant results regarding the primary outcomes or severe adverse events.

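### Three unadjusted looks at p<0.05 with stopping at the first significant interim roughly double the type I error on each primary outcome

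*Combined protocol and SAP*

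**What the plan says.** The Statistical analysis section states that "a p-value of <0,05 will be considered significant" and gives no other level for interim or final tests. A first interim analysis is planned at 35 infants per arm, and "Another interim analysis will be conducted when 65 infants have been recruited in each study arm". The stopping rule is: "The study will be discontinued as soon as an interim analysis shows statistically significant results regarding the primary outcomes or severe adverse events". Looks outside the schedule are also allowed: "Unplanned interim analysis will also be conducted in case of subjectively estimated too obvious difference between the groups", with the primary outcomes named as the trigger.

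The end of recruitment is set under Completion of the study: "The study will be completed when the number of 100 subjects per study arm is reached", with up to 130 per arm permitted. There are two primary outcomes, TFF and "NEC, Bell stage II or more". For TFF the plan is specific: "Times to achieve full enteral feeding will be compared by the log rank test". For categorical outcomes such as NEC it names chi-square or Fisher's exact test without saying which applies when.

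The sample size section intends a 5% error level: "For study power of at least 70%, confidence level of 5" percent. The Ethical considerations section mentions predefined stopping rules, but for adverse events. Its criterion for stopping on benefit is an impression with no number attached.

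**The concern.** Each look at p<0.05 is a further chance of a false positive, and the plan makes the first one end the trial. The 5% level in the sample size section then describes only a trial analysed once. The trial is also unmasked, so a chance imbalance can be noticed and can itself prompt an extra look.

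Two ambiguities make the error rate hard to state. The stopping sentence does not say whether one or both primary outcomes must be significant, and the NEC test at each look is not fixed.

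At stake is an early stop on a chance finding, usually with fewer infants than planned for NEC and safety, in favour of a twice-daily invasive procedure in infants born at 22+0 to 26+6 weeks.

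**Working it through.** **Inputs.** From the documents: looks at 35, 65 and 100 per arm, 1:1 allocation, p<0.05 at each, control NEC rate 15%, target rate 8%. Assumptions: tests are two-sided (sidedness is not stated), and information grows in proportion to recruitment, giving fractions t = 0.35, 0.65 and 1.

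**The plan's own figure.** One analysis at |Z|>1.96 gives the stated 5.0% (2.5% in the benefit direction).

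**Large-sample error over three looks.** Under no effect the statistics are jointly normal with corr(Zi, Zj) = sqrt(ti/tj):
- looks 1 and 2: sqrt(0.35/0.65) = 0.734
- looks 1 and 3: sqrt(0.35) = 0.592
- looks 2 and 3: sqrt(0.65) = 0.806

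Error = 1 − P(|Z1|≤1.96, |Z2|≤1.96, |Z3|≤1.96). Numerical integration gives 5.0% at 35 per arm, 8.2% by 65 and 10.7% overall.

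**The planned tests.** NEC figures are exact, enumerating both binomial counts across the looks. Log rank figures are from 60,000 simulated trials with exponential times. The censored case puts the looks at the 70th and 130th recruit with 49 infants a year (70 × 70%, from the sample size section), and assumes a mean TFF of 14 days and 13% dying first.

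| No true effect | One analysis | Three looks | Benefit direction |
|---|---|---|---|
| Large-sample | 5.0% | 10.7% | 5.3% |
| TFF log rank, no censoring | 5.2% | 11.4% | 5.6% |
| TFF log rank, censoring and deaths | 5.2% | 11.5% | 5.7% |
| NEC chi-square, 15% both arms | 5.1% | 10.9% | 5.4% |
| NEC chi-square, 8% both arms | 5.1% | 11.3% | 5.6% |
| NEC Fisher, 15% both arms | 3.3% | 6.1% | 3.1% |
| NEC Fisher, 8% both arms | 2.7% | 4.3% | 2.2% |

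A separate log rank simulation with gamma-distributed times and about 10% of infants subject to random censoring gave 11.3%. If Fisher is used only when an expected count is below 5 (a common convention the plan does not state), NEC error is 7.8% at an 8% rate and 9.9% at 15%.

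**Readings of the stopping rule.** Large-sample error per outcome, for an assumed correlation of 0 to 0.7 between outcomes:
- either outcome stops the trial: 10.3% down to 10.1%, slightly lower because a stop on one outcome removes later looks at the other;
- both must be significant to stop, otherwise each is tested once at the end: 5.3% up to 6.8%.

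**Larger trial.** A final analysis at 130 instead of 100 per arm gives 11.2%. Looks at 35, 65, 100 and 130 give 12.5%.

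**Example boundary.** Two-sided spending is 4 × [1 − Φ(2.241/√t)], that is 0.0003, 0.0109 and 0.05 cumulatively. The limits are |Z| > 3.613, 2.550 and 1.990, or nominal p of 0.0003, 0.011 and 0.047. Overall error is 5.0% for one outcome alone. In large-sample simulation it is 4.8% to 5.0% if either outcome stops the trial and 4.7% if both must.

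**The case against.** The strongest reply is that 11% is an isolated-outcome figure. The plan refers to the primary outcomes in the plural, and if both must be significant the error per outcome is only 5.3% to 6.8%. For NEC, Fisher's test keeps the error near or below 5%, and at 35 per arm small expected counts would often lead an analyst to it. These points stand as limits on size. They do not restore control: the plan selects neither reading, both exceed 5% in the large-sample calculation, and Fisher does nothing for TFF. Fisher's apparent control of NEC comes from its conservatism, since a single analysis would run at about 3%.

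A second reply concerns harm. As written, a significant excess of NEC in the lavage arm also stops the trial, and a strict boundary applied symmetrically would weaken that. At 35 per arm with 5 control cases, chi-square reaches p<0.05 at 13 intervention cases but p<0.0003 only at 20. With an assumed 15% versus 25%, the chance of stopping for harm by 65 per arm would fall from 34% to 13%. This is a sound reason to confine the boundary to efficacy. It is no argument for unadjusted efficacy testing.

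**Conclusion.** The concern holds. As written, the plan does not deliver its 5% level. Taken alone, each primary outcome has a two-sided type I error of about 11% by log rank (TFF) or chi-square (NEC), of which about 8.2 percentage points arise by 65 per arm. The error is about 4% to 6% for NEC if Fisher is always used, and 5.3% to 6.8% per outcome if stopping needs both outcomes.

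The figures assume two-sided tests, information proportional to recruitment and a final analysis at 100 per arm. They exclude the unplanned looks, whose effect the documents do not allow anyone to calculate, so they understate the error under the full rule. They also exclude multiplicity across the two primary outcomes. This must be corrected before any interim analysis is used to stop the trial for efficacy.

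**What to change.** - Prespecify a group sequential efficacy boundary for each primary outcome. The O'Brien-Fleming-type Lan-DeMets example above is one choice, and other valid boundaries would do. Fix the size of the final analysis (100, or up to 130 per arm), because the information fractions depend on it.
- State whether one or both primary outcomes trigger stopping, the sidedness of the tests, and the NEC test at each look.
- Delete the impression-triggered efficacy looks. Any added efficacy look should have timing independent of the outcome data and spend from the same function. Tie the benefit criterion in Ethical considerations to the same boundary.
- State that the efficacy boundary does not limit the safety monitoring committee's review of harm, including excess NEC, and whether NEC falls under its predefined rules.
- Handle multiplicity across the two primary outcomes separately. This change controls error per outcome only.

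**Cost.** Protocol wording, a final threshold of about 0.047 instead of 0.05, and fewer early efficacy stops. The table uses an unchanged 100 per arm. The first two rows assume an effect of the stated power, and the third is the plan's own NEC effect.

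| Effect | Power, single analysis | Power, boundary | Stop by 65 at p<0.05 | Stop by 65, boundary |
|---|---|---|---|---|
| Assumed, 70% power | 70% | 69.5% | 56% | 29% |
| Assumed, 80% power | 80% | 79.5% | 65% | 39% |
| NEC 15% vs 8%, chi-square | 35% | 34% | 29% | 8% |

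The third row shows that 100 per arm does not give the stated 70% power for NEC. That is a separate problem, and it does not affect the type I error result.

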## **Ethical considerations**

The study protocol will be submitted for approval to the Regional Ethical Review Board in Uppsala and subsequently registered at the international registry of clinical trials, ClinicalTrials.gov. The parents of the infants will be informed about the study by specially trained personnel, both verbally and in writing, before the child is born or, whenever that is not possible, as soon as possible after birth. Upon agreement to participate, written informed consent will be obtained from the parents, before enrollment in the study. Additionally, the parents will be clearly informed about the possibility to leave the study any time they wish.

None of the studies published so far reported any adverse events by induced meconium evacuation, with the exception of a higher proportion of NEC (although not statistically significant), vomiting, nausea and bradycardia with the use of oral gastrografin (1,22), and a non-significant trend towards increased risk of NEC with the use of glycerine enemas or suppositories compared with no treatment (25). However, in the RCT study described herein, both health personnel involved in the participating infants' daily care and the investigators are going to closely monitor for possible adverse events. Possible adverse events could be: rectal bleeding (including occult rectal bleeding-induced anemia), fluid loss due to overstimulation of immature intestines of preterm infants or the opposite effect, namely intestinal absorption of given saline, leading to hypervolemia and electrolyte disturbances, mainly hyponatremia. A safety monitoring committee will monitor adverse events with predefined stopping rules. Early stopping criteria will be applied in case of medical instability, as mentioned above. Furthermore, the whole study will be discontinued in case of too obvious positive effect, making it unethical to deprive the control group of the intervention, or in case of severe adverse events.

The inclusion of study participants in other interventional studies could intervene with the outcomes intended to be investigated in the study herein, rendering it difficult to retrieve definitive conclusions. Thus, study participants will not be included in other interventional studies at the same time.

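### Two unranked primary outcomes are tested at unadjusted p<0.05 at every look with no either/both rule, and the 5% level fails whether one or both must be significant

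*Combined protocol and SAP*

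**What the plan says.** The Primary outcomes section of the combined protocol and SAP lists two items, with no order between them: "TFF, defined as the period between birth and achievement of enteral nutrition of 170ml/kg/d" and "NEC, Bell stage II or more".

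The Statistical analysis section gives one significance level for everything: "a p-value of <0,05 will be considered significant". It then schedules two looks: "Interim analysis will be conducted when 35 infants have been recruited in each study arm" and "Another interim analysis will be conducted when 65 infants have been recruited in each study arm". It adds looks with no fixed timing: "Unplanned interim analysis will also be conducted in case of subjectively estimated too obvious difference between the groups regarding the primary outcomes". The consequence of a significant look is "The study will be discontinued as soon as an interim analysis shows statistically significant results regarding the primary outcomes or severe adverse events".

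Ethical considerations adds a further efficacy stop with no threshold: "the whole study will be discontinued in case of too obvious positive effect". The same section mentions predefined stopping rules held by a safety monitoring committee, but these concern adverse events.

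No section splits alpha between the outcomes, orders them, or sets a boundary for benefit at a look. The sample size section is based on NEC because it is the rarest event. That is a sizing choice, not a testing order.

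**The concern.** Two sources of error inflation are present and neither is controlled: two primary outcomes, and repeated testing of accumulating data with a stop at the first significant result. The trial is unmasked, so visible differences between the arms can themselves trigger an extra look.

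The size of the problem depends on a rule the plan does not state, namely whether one significant primary outcome is enough to stop and claim success or both are needed. Until that is fixed, no error rate can be attached to the trial's claim. A false positive at 35 or 65 per arm would end recruitment early and be reported as a primary result on NEC or on feeding in infants born at 22 to 26 weeks.

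**Working it through.** **The plan's own figure.** The documents state a 5% level but no overall type I error for the interim plan, so there is no overall figure to reproduce. The check asks what error the stated rule gives.

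**Inputs from the documents.** Looks at 35 and 65 per arm and a final analysis at 100 per arm; p<0.05 at each; two primary outcomes; NEC 15% versus 8% (sample size section).

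**Assumptions.** Tests are two-sided with |Z|>1.96 (sidedness is not stated). Outcomes are known for every recruited infant at each look. The correlation ρ between the two test statistics runs from 0 to 0.8 (none is given). The hazard ratios (HR) for TFF are also assumed.

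**Method.** Information fractions are t = 0.35, 0.65 and 1. For each outcome Z(t) = W(t)/√t, where W has independent normal increments, so looks j<k correlate at √(t_j/t_k): 0.73, 0.59 and 0.81. The two outcomes' increments correlate at ρ. Each setting used 1 million simulated trials.

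**Each source of inflation alone, no true effect on either outcome.**
- Two outcomes, final analysis only: 1 − 0.95² = 9.75% at ρ = 0, falling to about 8% at ρ = 0.8.
- One outcome, three looks: 10.7%.

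***Either* reading, three looks, no true effect.** At ρ = 0 the error is 1 − (1 − 0.107)² ≈ 20.2%.

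| ρ | 0 | 0.5 | 0.8 |
|---|---|---|---|
| Either significant at any look | 20.2% | 18.8% | 16.2% |
| Both significant at the same look | 0.7% | 2.2% | 5.0% |

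With NEC always tested by Fisher's exact test, which is conservative at these counts, the *either* error is 16.0% to 14.4% for a null NEC rate of 15% and 14.3% to 13.8% for 8%.

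***Both* reading, one outcome truly improved.** The last row of the table covers only the case where neither outcome responds. A false *both* claim also arises when TFF improves and NEC does not. The TFF drift is ln(HR)·√(events/4). With 180 events (90% of 200 infants, assumed) it is 0.405 × 6.71 = 2.72 at HR 1.5, 4.65 at HR 2.0 and 7.37 at HR 3.0. NEC has no effect.

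| HR for TFF | False *both* claims, ρ = 0 to 0.8 |
|---|---|
| 1.5 | 6.7% to 5.5% |
| 2.0 | 9.9% to 8.3% |
| 3.0 | 10.6% to 10.4% |

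As TFF becomes certain to be significant, the rule reduces to NEC alone over three looks, whose error is the 10.7% above.

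**Unplanned looks.** The plan gives no timing. Purely as illustration, one extra look at 50 per arm raises the *either* error to 18–22%.

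**Candidate boundary.** O'Brien–Fleming at two-sided 0.025 per outcome has a final critical value of 2.27, so the looks use 2.27/√0.35 = 3.84, 2.27/√0.65 = 2.82 and 2.27. Simulated error is 2.5% per outcome and 4.0–4.9% for either outcome (ρ = 0.8 to 0).

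**Power.** Assumed HR 1.5 with 180 events; NEC drift 0.07/√(2 × 0.115 × 0.885/100) = 1.55; ρ = 0.5 to 0. The single-outcome rows allow for the trial stopping when the other outcome crosses.

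| | p<0.05 at each look | Boundary |
|---|---|---|
| At least one correct claim | 84–89% | 70–76% |
| TFF | 72–76% | 65–66% |
| NEC | 27–28% | 17–19% |

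**The case against.** The strongest reply is that the trial may intend both outcomes to be significant. The Study hypothesis section presents one causal chain, in which faster feeding lowers the risk of sepsis and NEC, and the stopping sentence uses the plural. That is fair: *either* is the likelier reading, but a reader who infers that the plan says so goes beyond the text. The 16–20% is therefore conditional.

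A reader might then infer that *both* makes the unadjusted looks safe. It does not. The low figures hold only when neither outcome is affected, and the plan's own hypothesis makes an effect on TFF the expected case.

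The correlation is unknown and some positive link is plausible, since feeds are resumed only after NEC has been ruled out. Under *either*, however, even perfect correlation leaves the single-outcome 10.7%. Delay between recruitment and outcome would shift the information fractions without removing the repeated testing.

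Two further inferences are not supported. The ceiling of 130 per arm in the Completion of the study section is not a plan to analyse at 100 and then extend; replacement of dropouts is a natural explanation. Nor does the plan lack safety stopping rules: it says that they are predefined, but for adverse events, so they do not limit claims of benefit.

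**Conclusion.** The concern holds under both readings and must be fixed. If either outcome suffices, the nominal 5% becomes about 16–20% over the planned looks, or about 14–16% with Fisher's test throughout. If both are required at the same look, false claims run at about 5–7%, 8–10% and 10.5% for assumed TFF hazard ratios of 1.5, 2.0 and 3.0 with no NEC effect, approaching the single-outcome limit of about 11%.

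These figures rest on two-sided tests, complete outcomes at each look, a final analysis at 100 per arm and the assumed correlations. They are not ceilings, because unplanned looks add to them by an amount the documents do not allow one to fix.

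**What to change.** 1. In Statistical analysis, state whether success needs either or both outcomes. If either, control alpha across them, for example by Holm or a fixed order.
2. Under either choice, replace p<0.05 at the looks with a prespecified group-sequential boundary for benefit at the alpha allotted to each outcome. With 0.025 two-sided per outcome, O'Brien–Fleming gives Z of about 3.84, 2.82 and 2.27 at 35, 65 and 100 per arm. Recompute from a spending function if the looks or final size change.
3. State which outcome or outcomes must cross to stop for efficacy. This is the sponsor's choice.
4. Bring the unplanned looks, and the unquantified efficacy stop in Ethical considerations, under the same boundary.
5. State that the boundary is for benefit only, and that harm, including excess NEC in the lavage arm, stays with the safety monitoring committee's predefined rules.

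The cost is a short paragraph in Statistical analysis, a matching sentence in Ethical considerations, no new data, and some power. Under the assumptions above, the chance of at least one correct claim falls by about 13–14 percentage points. Part of that loss is the price of removing inflated error rather than a true loss of efficiency.

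### As written, a significant time-to-full-feeds result alone can end the trial at 35 or 65 per arm, fixing NEC power at about 16% or 24%, against about 35% at full size

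*Combined protocol and SAP*

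**What the plan says.** Primary outcomes lists two, without ranking them: "TFF, defined as the period between birth and achievement of enteral nutrition of 170ml/kg/d" and "NEC, Bell stage II or more".

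The sample size section uses only the second: "Sample size calculation is based on the incidence of NEC, as the rarest of the events that will be studied". It assumes a fall from 15% to 8%, a 5% level and at least 70% power, and concludes that "each study arm should include about 100 participants".

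Statistical analysis plans looks at 35 and 65 per arm and allows unplanned ones. Its rule is "The study will be discontinued as soon as an interim analysis shows statistically significant results regarding the primary outcomes"; the same sentence adds severe adverse events as a ground. The only significance level given is p<0.05, with no interim adjustment. Ethical considerations adds that "the whole study will be discontinued in case of too obvious positive effect". Nothing in the document keeps recruitment open for NEC once TFF is significant, and nothing says that both outcomes must be significant.

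**The concern.** The outcome that sets the sample size is not the only one that can end the trial. The unit aims for full feeds within about 5 to 10 days, so nearly every infant supplies a TFF event early, whereas NEC is expected in 15% or fewer. TFF therefore carries much more information per infant. If lavage does shorten TFF, as the hypothesis states, the trial may close with a feeding result and a thin comparison of NEC, sepsis, mortality and harms.

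The safety side matters. Ethical considerations itself reports a non-significant trend to more NEC with glycerine enemas or suppositories. TFF is also a weak sole basis for closing an open-label trial in which feeds are advanced on an individual basis.

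**Working it through.** **Inputs.** From the document: NEC 15% against 8%; 1:1 allocation; looks at 35 and 65 per arm, planned end at 100; p<0.05; log-rank test for TFF; chi-square or Fisher's exact test for NEC. Assumed: two-sided tests; every infant has reached full feeds by the look; TFF hazard ratios (HR above 1 means faster feeding) of 1.2, 1.5 and 2.0, because the plan states no TFF effect.

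**1. The plan's own figure.** n per arm = [1.96·√(2·0.115·0.885) + 0.524·√(0.15·0.85 + 0.08·0.92)]² / 0.07² = (0.884 + 0.235)² / 0.0049 ≈ 256 for 70% power. A one-sided test needs 195. About 100 per arm is not reproduced. At 100 per arm, two-sided power is 34% by this formula and 35% by exact enumeration of the chi-square test. So the comparator for early stopping is about 35%, not 70%.

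**2. Chance of stopping on TFF.** The log-rank statistic is roughly normal with mean ln(HR)·√(events/4). With 70 and 130 events the means are:

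- HR 1.2: 0.182·4.18 = 0.76, and 0.182·5.70 = 1.04
- HR 1.5: 0.405·4.18 = 1.70, and 0.405·5.70 = 2.31
- HR 2.0: 0.693·4.18 = 2.90, and 0.693·5.70 = 3.95

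The correlation between looks is √(70/130) = 0.73. The O'Brien-Fleming-type critical values for the three analyses are 3.38, 2.48 and 2.00 at 5%, and about 3.83, 2.81 and 2.27 at 2.5%. The probability of crossing by the second look is:

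| HR | p<0.05 at each look | O'Brien-Fleming type, 5% | O'Brien-Fleming type, 2.5% |
|---|---|---|---|
| 1.2 | 22% | 7.5% | 4% |
| 1.5 | 67% | 43% | 31% |
| 2.0 | 98% | 93% | 87% |

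At p<0.05 the first look alone gives 40% (HR 1.5) and 83% (HR 2.0). If only 70% of infants reach full feeds, stopping by the second look at p<0.05 is still 53% (HR 1.5) and 92% (HR 2.0).

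**3. What is left for NEC and harms.** Power is by binomial enumeration. The 95% CI half-width is 1.96·√[(0.15·0.85 + 0.08·0.92)/n]. The upper bound after zero cases of a harm in the lavage arm is 1 − 0.05^(1/n).

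| Per arm | Expected NEC cases | Power, chi-square (Fisher) | Half-width, points | Bound after zero cases |
|---|---|---|---|---|
| 35 | 5.3 v 2.8 | 16% (7%) | 15 | 8.2% |
| 65 | 9.8 v 5.2 | 24% (16%) | 11 | 4.5% |
| 100 | 15 v 8 | 35% (27%) | 9 | 3.0% |

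At 35 per arm the mean expected count is about 4 per arm, so Fisher's test would probably be used and the 16% is generous.

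**The case against.** The rule refers to the primary outcomes in the plural. A reader might infer that TFF alone certainly ends the trial. The text does not say "either", and a both-required reading is possible, although nothing in the document supports it. What stands is that TFF alone can end the trial as the rule is written.

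A reader might also infer that TFF will almost always cross first. The figures do not support that for a modest effect: 22% at HR 1.2 with no adjustment, and 43% at HR 1.5 with a proper boundary. The HR of 2.9 in the Background comes from an observational study of glycerine enema, while several trials and meta-analyses cited there found no reduction in TFF. Nor is the problem independent of the interim alpha, since the unadjusted 67% at HR 1.5 falls to 31% once the alpha is split and a boundary applied. It persists where the TFF effect is substantial.

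NEC is not abandoned. Follow-up collects NEC, sepsis and mortality to 40+0 weeks for enrolled infants, and a safety committee is to work with predefined stopping rules. Early stopping is also not the main reason why NEC would go unanswered, because full enrolment gives only about 35% power.

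Finally, TFF is a full primary outcome, and the plan offers an ethical reason to stop for benefit. That is a legitimate choice, but it conflicts with sizing the trial on NEC, and the plan does not acknowledge the conflict.

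**Conclusion.** The concern holds in a limited form: the stopping rule permits an outcome that did not set the sample size to close the trial. With a substantial TFF effect (HR 2.0) this is likely under any of the three boundaries examined; at HR 1.5 it is roughly one chance in three to two in three; at HR 1.2 it is uncommon once alpha is controlled. Closing then costs 11 to 19 points of NEC power (35 − 24 and 35 − 16), widens the interval by 2 to 6 points each side, and raises the harm rate that zero cases can exclude from 3.0% to 4.5% or 8.2%.

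These sizes rest on two-sided testing, the plan's NEC rates, proportional hazards, nearly complete TFF data at each look and assumed TFF effects. Unplanned looks could bring the stop at other sample sizes. The change should be made, but it does not repair the sample size.

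**What to change.** In Statistical analysis, state that:

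- a TFF result alone cannot end recruitment, and TFF is tested once, at completion;
- early stopping for benefit rests on NEC against a group-sequential boundary, which must be added because the plan has none;
- stopping for severe adverse events remains, and a significant excess of NEC in the lavage arm counts as a harm signal, so that limiting the benefit rule to NEC does not drop that protection.

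Bring the sentence on stopping for an obvious benefit in Ethical considerations into line.

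This is a wording change and needs no infants beyond the planned 100 per arm. The cost is that early stopping for benefit becomes unlikely: with the 5% boundary above and NEC at 15% against 8%, the chance of crossing is about 0.2% at the first look and 9% by the second. Controls would stay on routine care to the planned size even if a feeding benefit appeared early. The sponsor should state that it accepts this.
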